17.4.1 Conversion from in person to remote study visits	119
17.4.2 Components of study visits that can be carried out remotely	120
17.4.3 Components of study visits that cannot be carried out remotely.....	120
17.5 Revised site monitoring	121
18 LITERATURE REFERENCES.....	125
APPENDIX LIST	125

LIST OF ABBREVIATIONS

AE	Adverse Event
ACR	American College of Rheumatology
ADL	Activities of daily living
ALT	Alanine Aminotransferase
ANC	Absolute Neutrophil Count
ANCOVA	Analysis of Covariance
AST	Aspartate Aminotransferase
ATS	American Thoracic Society
AUC	Area under the curve
BID	Twice daily
BDI	Baseline Mahler Modified Dyspnea Index
BAL	Bronchoalveolar lavage
BUN	Blood Urea Nitrogen
CDC	Center for Disease Control
CFR	Code of Federal Regulations
CLIA	Clinical Laboratory Improvement Amendments
Cmax	Maximum concentration
CMP	Clinical monitoring plan
CMV	Cytomegalovirus
COVID-19	Coronavirus Disease 2019
Cr	Creatinine
CRF	Case Report Form
CRISS	Combined Response index in Systemic Sclerosis
CTCAE	Common Terminology Criteria for Adverse Events V4.03-2010
CYC	Cyclophosphamide
CYP	Cytochrome P450
DCC	Data Coordinating Center
DLCO	Single-Breath Diffusing Capacity of the Lung for Carbon Monoxide
DLCO-Hb-%	DLCO, adjusted for age, height, gender and hemoglobin
DMARD	Disease-modifying antirheumatic drug
DSMB	Data Safety Monitoring Board
ECG	Electrocardiogram
eCRF	Electronic Case Report Forms
ERS	European Respiratory Society
EULAR	European League Against Rheumatism
FEV1	Forced Expiratory Volume in the first second
FDA	Food and Drug Administration
FVC	Forced vital capacity
FVC-%	Forced vital capacity as a percentage of the age-, height-, gender- and race-adjusted predicted value
GERD	Gastroesophageal reflux disease
GCP	Good Clinical Practice
GOO	Ground glass opacification

GLP	Good Laboratory Practices
GMP	Good Manufacturing Practices
H&P	History and physical
HBV	Hepatitis B virus
HCV	Hepatitis C virus
Hgb	Hemoglobin
HIPAA	Health Insurance Portability and Accountability Act
HRCT	High resolution computerized tomography
HRCT-TLC	HRCT-measured total lung capacity at maximum inspiration
HRQoL	Health-related quality of life
IB	Investigator's Brochure
IFN- γ	Interferon-gamma
ILD	Interstitial lung disease
IND	Investigational New Drug Application
IPF	Idiopathic pulmonary fibrosis
IRB	Investigational Review Board
JC	Polyomavirus JC
LCQ	Leicester Cough Questionnaire
LFTs	Liver function test
MCP-1	Macrophage chemotactic protein-1
MCTM	Markov Chain Transition Matrix
MITT	Modified intention to treat
MPA	Mycophenolic acid
MPAG	phenolic glucuronide metabolite of MPA
MMF	Mycophenolate mofetil; same as CellCept
MMP	Matrix metalloproteinase
MOP	Manual of Procedures
mRSS	Modified Rodnan Skin Score
NIH	National Institutes of Health
NSIP	Non-specific interstitial pneumonia
OHRP	Office for Human Research Protections
PAH	Pulmonary arterial hypertension
PDGF	Platelet derived growth factor
PFD	Pirfenidone; same as Esbriet
PFT	Pulmonary function test
PI	Principal Investigator
Plac	Placebo
PML	Progressive multifocal leukoencephalopathy associated with JC virus
PP	Per protocol
PPI	Proton pump inhibitors
PRCA	Pure Red Cell Aplasia
PRO	Patient Reported Outcome
PROMIS-29	Patient-reported outcomes measurement information system 29-item health profile
PVAN	Polyomavirus associated nephropathy
QA	Quality Assurance
QC	Quality Control

QGG	Quantitative ground glass
QHC	Quantitative honeycomb change
QIA	Quantitative image analysis
QILD-LM	Quantitative interstitial lung disease score in the lobe of maximal involvement
QILD-WL	Quantitative interstitial lung disease score in the whole lung
QLF-LM	Quantitative lung fibrosis score in the lobe of maximal involvement
QLF-WL	Quantitative lung fibrosis score in the whole lung
SABER	Statistical Analysis of Biomedical and Educational Research Unit
SAE	Serious Adverse Event
SAP	Statistical Analysis Plan
SGRQ	St. George's Respiratory Questionnaire
SHAQ	Scleroderma Health Assessment Questionnaire
SLS	Scleroderma Lung Study
SMC	Safety Monitoring Committee
SOC	System Organ Class
SOP	Standard Operating Procedure
SSc	Scleroderma (same as Systemic Sclerosis)
SSc-lc	Scleroderma with limited cutaneous features
SSc-dc	Scleroderma with diffuse cutaneous features
SSc-ILD	Scleroderma-related interstitial lung disease
TDI	Transitional Mahler Modified Dyspnea Index
TEAE	Treatment-emergent adverse event
TGF- β 1	Transforming growth factor beta-1
TID	Three times daily
UCLA SCTC GIT 2.0	University of California, Los Angeles, Scleroderma Clinical Trials Consortium Gastrointestinal Scale
UIP	Usual interstitial pneumonia
ULN	Upper limit of normal
UP	Unanticipated Problem
US	United States
WBC	White blood cell

STATEMENT OF COMPLIANCE

This trial will be conducted with Good Clinical Practice (GCP) and in accordance with the Code of Federal Regulations on the Protection of Human Subjects (21 CFR Part 50). The Principal Investigator will assure that no deviation from, or changes to the protocol will take place without documented approval from the applicable Institutional Review Boards (IRBs), except where necessary to eliminate an immediate hazard(s) to the trial participants. All personnel involved in the conduct of this study have completed Human Subjects Protection Training.

I agree to ensure that all staff members involved in the conduct of this study are informed about their obligations in meeting the above commitments.

Principal Investigator:

[name]. (Print/Type Name)

Signed:

(Signature)

Date: 11/17/2021 (version 2.5)

PROTOCOL SUMMARY

Title:	SCLERODERMA LUNG STUDY III (SLS III)
Précis:	A Phase II multi-center, double-blind, parallel group, randomized and placebo-controlled clinical trial addressing the treatment of patients with active and symptomatic Scleroderma-related interstitial lung disease (SSc-ILD). 150 patients who are either treatment naïve or only recently started treatment (≤ 6 mo of prior treatment with a potentially disease-modifying therapy) will be randomized in a 1:1 assignment to receive either oral mycophenolate mofetil (MMF) and a placebo (Plac) or a combination of oral MMF and oral pirfenidone (PFD), with both regimens administered for 18 months. The primary assessment will be the change from baseline over the 18 month treatment period, as measured at 3-month intervals, in the course of the Forced Vital Capacity measured as a percentage of the age-, height-, gender- and race-adjusted predicted value (FVC-%). Key secondary outcomes will include changes over time in dyspnea, skin score, diffusing capacity and high resolution computerized tomography (HRCT) measures of interstitial lung disease ILD). Tolerability and toxicity of the two treatments will also be assessed.
Objectives:	Primary Hypothesis: The primary hypothesis is that the rapid onset and anti-fibrotic effects of PFD, which have been observed in the treatment of Idiopathic Pulmonary Fibrosis (IPF), will complement the delayed anti-inflammatory and immunosuppressive effects of MMF, to produce a significantly more rapid and/or greater improvement in lung function over time than occurs in patients receiving control therapy with MMF and Plac. A secondary objective is to demonstrate that combination therapy with PFD and MMF is well tolerated, in comparison to MMF alone, and not associated with limiting toxicity that impacts on the overall treatment effect.
Endpoints	Primary Endpoint: The primary endpoint is the change from baseline, measured at 3-month intervals, in the mean forced vital capacity (represented as the percentage of the age-, height-, gender- and race-adjusted predicted value, i.e. FVC-%) over the course of the 18-month double-blind treatment period. Pre-specified Secondary Endpoints: 
1. The change from baseline to 18 months, measured at 3-month intervals, in the following disease measures:
• Single-breath diffusing capacity for carbon monoxide (DLCO), calculated as a percent of the age-, height-, gender-, race- and hemoglobin-adjusted predicted value (DLCOHb-%).

	
• Modified Rodnan Skin Score (mRSS).• Transitional Mahler Modified Dyspnea Index (TDI).• Patient Reported Outcomes (PROs), which provide subjective measures of dyspnea and quality of life based on patient responses to standardized patient questionnaires. 
2. The change from baseline to 18 months in HRCT measures of SSc-ILD:
 
• Quantitative lung fibrosis score in the whole lung (QLF-WL).• Quantitative lung fibrosis score in the lobe of maximal involvement (QLF-LM).• Quantitative interstitial lung disease score in the whole lung (QILD-WL).• Quantitative interstitial lung disease score in the lobe of maximal involvement (QILD-LM).• Total lung capacity at maximum inspiration (HRCT-TLC) 
3. Differences in the frequency distribution of individual patient responses when grouped into defined intervals of improvement or worsening (defined by the change in an outcome measure from baseline to 18 months) for the following outcome measures:
 
• Forced vital capacity (represented as the percentage of the age-, height-, gender- and race-adjusted predicted value, i.e. FVC-%)• Single-breath diffusing capacity for carbon monoxide (DLCO), calculated as a percent of the age, height, gender and hemoglobin adjusted predicted value (DLCOHb-%).• Modified Rodnan Skin Score (mRSS).• Transitional Mahler Modified Dyspnea Index (TDI) 
4. The time (in months) required for each treatment arm to achieve a 3.0% or greater improvement from baseline in the FVC-% over the 18-month treatment period.
 
5. A threshold analysis based on the percentage of subjects in each treatment arm achieving greater than a 5% improvement in FVC-% over the 18-month treatment period.
 
6. Tolerability and toxicity of MMF+Plac versus MMF+PFD over the course of 18 months.

Population:	150 randomized participants from recruitment sites in the United States, including both male and female patients of an age ≥ 18 years, diagnosed with systemic scleroderma (SSc) as defined by the 2013 American College of Rheumatology (ACR)/European League Against Rheumatism (EULAR) classification criteria, who demonstrate evidence of active restrictive lung disease by pulmonary function testing, symptomatic dyspnea and any evidence of ground glass opacification (GGO) on baseline thoracic HRCT, and who meet the study definition of being either treatment naïve or recently started on treatment (≤ 6 mo of prior treatment with a potentially disease-modifying therapy) and all other inclusion & exclusion criteria as detailed below.

[figure not shown]
Phase:	Phase II
Number of Sites enrolling participants:	Between 15 to 25 participating clinical sites Please see Section 1, Key Roles, for a current list of participating sites
Description of Study Agents:	
1. Mycophenolate Mofetil (MMF) Manufactured by: Teva Pharmaceuticals, Inc (Generic) Oral Route 250 mg capsules Target Dose: 1500 mg twice daily as tolerated with a 4-step titration at monthly intervals
 
 500 mg (two capsules) twice daily (BID) for 4 weeks 1000 mg (four capsules) BID for 4 weeks 1250 mg (five capsules) BID for 4 weeks 1500 mg (six capsules) BID for remainder of study as tolerated. 
2. Pirfenidone (PFD), same as Esbriet® Manufactured by: Genentech, Inc. Oral Route 267 mg capsules. Target Dose: 801 mg three times daily as tolerated with a 3-step titration at 2 week intervals:
 
 267 mg (one capsule) three times daily (TID) for 2 weeks 534 mg (two capsules) TID for 2 weeks 801 mg (three capsules) TID for remainder of study as tolerated. 
3. Placebo (Plac), matching to the PFD capsules Manufactured by: Genentech, Inc. Oral Route 267 mg capsules. Target Dose: 801 mg three times daily as tolerated with a 3-step titration at 2 week intervals:
 
 267 mg (one capsule) three times daily (TID) for 2 weeks 534 mg (two capsules) TID for 2 weeks 801 mg (three capsules) TID for remainder of study as tolerated.
Study Duration:	Approximately 4 years total study duration, sub-divided into the following components: 
 24 month enrollment period 18-month randomized, double-blind treatment period per patient 1 month follow-up period after completion of drug therapy 6 month primary analysis period
Participant Duration:	20-22 month subject participation period made up of the following components:

	
 - screening = 1-3 months - randomized, double-blind treatment period = 18 months - final follow-up period after completion of drug therapy = 1 month
Inclusion Criteria:	
 1. Age \geq18 yrs 2. Scleroderma as determined by the 2013 ACR/EULAR classification criteria. 3. Grade \geq2 on the Magnitude of Task component of the Mahler Modified Dyspnea Index (Becomes short of breath with moderate or average tasks such as walking up a gradual hill, climbing less than three flights of stairs, or carrying a light load on the level.) 4. FVC-% of \leq85% at screening. 5. Onset of the first non-Raynaud manifestation of SSc within the prior 84 months. 6. Presence of any GGO on thoracic HRCT 7. Repeat FVC-% at the baseline visit within 10% of the FVC-% value measured at screening. If these criteria are not met, a repeat FVC-% may be obtained within 7 days and the subject may qualify for randomization if the repeat FVC-% agrees within 10% of the FVC-% obtained at screening.
Exclusion Criteria:	
 1. Disease features supporting the primary diagnosis of another connective tissue disease such as rheumatoid arthritis, systemic lupus erythematosus or mixed connective tissue disease (Features consistent with a secondary Sjogren syndrome or scleroderma-associated myopathy will be allowed). 2. FVC-% of $<$45% at either screening or baseline. 3. FEV1/FVC ratio $<$0.65 at either screening or baseline. 4. DLCOHb-% of $<$30% at screening or $<$25% at baseline. 
 a) All participants with a DLCOHb-% between 30 to 40% must have pulmonary artery pressures documented by either echocardiogram, right heart catheterization or magnetic resonance imaging in order to be considered for inclusion. 5. Diagnosis of clinically significant resting pulmonary hypertension requiring treatment or mild pulmonary hypertension requiring treatment with more than one oral medication as ascertained prior to study evaluation or as part of a standard of care clinical assessment performed outside of the study protocol. 6. Evidence of uncontrolled congestive heart failure, unstable ischemic heart disease, history of complicated pulmonary embolism impacting on heart or lung function, or unstable cardiac arrhythmia requiring chronic anticoagulation. 7. Clinically significant abnormalities on HRCT not attributable to SSc 8. Hematologic abnormality at screening including:

	
a) Leukopenia (white blood cells [WBC] $<4.0 \times 10^3/\mu\text{l}$) b) Thrombocytopenia (platelet count $<120.0 \times 10^3/\mu\text{l}$) c) Clinically significant anemia [Hemoglobin (Hgb) $<10.0 \text{ g/dl}$]
 
Participants with an identified and correctable etiology may be eligible if repeat testing within the maximal 90-day screening period meets all criteria.
 
9. A diagnosis of chronic liver disease or abnormal baseline liver function test (LFTs) or total bilirubin that are $>2.0 \times$ upper normal limit
 
10. Serum creatinine $>2.0 \text{ mg/dl}$
 
11. History of recurrent aspiration, uncontrolled heartburn, or gastroesophageal reflux disease (GERD) with a reflux scale score of >1.00 as determined by a UCLA Scleroderma Clinical Trial Consortium Gastrointestinal Scale (UCLA SCTC GIT), Version 2.0.
 
Participants with uncontrolled heartburn or GERD that is amenable to medical management may be eligible if repeat testing within the maximal 90-day screening period meets this criteria.
 
12. Known achalasia, esophageal stricture or esophageal dysfunction sufficient to limit the ability to swallow medication.
 
13. Pregnancy (documented by serum pregnancy test) and/or breast feeding
 
14. If of child bearing potential (a female participant <55 years of age who has not been postmenopausal for ≥ 5 years or who has not had a bilateral salpingectomy, hysterectomy and/or oophorectomy), failure to employ two reliable means of contraception which may include surgical sterilization, barrier methods, spermicides, intrauterine devices, and/or hormonal contraception, unless the participant chooses abstinence (to avoid heterosexual intercourse completely.) If a subject chooses abstinence, then a second reliable means of contraception is not needed.
 
15. Prior use of potential disease modifying antirheumatic drugs (DMARDs) according to the following exposure rules:
 
Use of oral cyclophosphamide (CYC), MMF, azathioprine or other oral or short half-life DMARDs (as detailed in Section 7.5.1a) for more than 6 months in the past year as determined at the time of the initial screening visit.Treatment with more than three intravenous doses of CYC, one treatment course of Rituximab or other intravenous or injectable DMARDs (as detailed in Section 7.5.1b) in the past year.More distant h/o treatment with a DMARD is allowed as long as the patient has a new diagnosis/new episode of active SSc-ILD since stopping that treatment and meets the criteria noted in 15a or 15b. 
16. Use of CYC, MMF, azathioprine, Rituximab or other DMARD (as detailed in Section 7.5.1a&b) in the 30 days prior to the baseline visit

--	--

	
unless the patient is on MMF and the responsible physician indicates that continued use is in the best clinical interest of the patient.
 
17. Active infection (lung, ulcers or elsewhere) whose management would be compromised by immunosuppression.
 
18. Other serious concomitant medical illness (e.g., active malignancy within the past 5 years other than surgically-removed local skin cancer such as a basal cell carcinoma), chronic debilitating illness (other than SSc), unreliability or drug abuse that might compromise the patient's participation in the trial.
 
19. Current use, or use within the 30 days prior to their baseline visit, of prednisone (or equivalent) in doses >10 mg/day.
 
20. Smoking of cigars, pipes, or cigarettes during the past 6 months.
 
21. Use of contraindicated medications, including medications with putative disease-modifying properties that do not meet the exposure limits described in Exclusion Criteria #15 and #16, moderate or strong inhibitors of cytochrome P450 (CYP) isozyme 1A2 (CYP1A2) (note ciprofloxacin allowed up to a dose of 500 mg twice daily), and moderate inducers of CYP1A2 (such as tobacco smoke, or phenytoin). See Section 7.5 for complete list.

--	--

SUMMARY SCHEMATIC OF STUDY DESIGN

SUMMARY TABLE OF STUDY VISITS AND ASSESSMENTS**

	Screen		Randomized Double-blind Phase																				Exit visit*	
	S1	S2	V1	V2	V3	V4	V5	V6	V7	V8	V9	V10	V11	V12	V13	V14	V15	V16	V17	V18	V19	V20	V21	
Visit #	Sc-1	Sc-2	0	0.5 (14 days) ±7d	1 (28 days) ±7d	1.5 (42 days) ±7d	2 (56 days) ±10d	3 (84 days) ±10d	4 (112 days) ±10d	5 (140 days) ±10d	6 (168 days) ±10d	7 (196 days) ±10d	8 (224 days) ±10d	9 (252 days) ±10d	10 (280 days) ±10d	11 (308 days) ±10d	12 (336 days) ±10d	13 (364 days) ±10d	14 (392 days) ±14d	15 (420 days) ±10d	16 (448 days) ±10d	17 (476 days) ±10d	18 (504 days) ±14d	V22
Month on Study (Month = 28 days)																								Month 19 (532 days) ±10d
Phone contact					X		X						X	X		X	X		X	X		X	X	X
On-Site Visit	X	X	X		X		X	X	X	X	X		X				X		X		X		X	
Complete H&P	X																							
F/u SSc-H&P			X		X		X	X	X	X	X		X											
Vital signs	X		X		X	X	X	X	X	X	X		X			X		X		X		X		
mRSS			X				X				X			X			X			X			X	
Study Consent	X																							
Adverse events			X	X	X	X	X	X	X	X	X	X	X	X	X	X	X	X	X	X	X	X	X	
Concomitant Medications	X		X	X	X	X	X	X	X	X	X	X	X	X	X	X	X	X	X	X	X	X	X	
Dispense meds			X		X	X	X	X	X	X	X			X			X			X				
Drug reconciliation			X		X	X	X	X	X	X	X			X			X			X			X	
Mahler BDI/TDI			X				X				X			X			X			X			X	
SGRQ			X				X				X			X			X			X			X	
SHAQ, PROMIS-29, UCLA SCTC GIT, CRISS, LCQ, Global Assessments	UCLA SCTC GIT		X (except CRISS)								X							X						X
LABS:																								
- CBC, diff, plat	X				X		X	X	X	X	X			X			X			X			X	
- Metabolic/liver	X				X		X	X	X	X	X			X			X			X			X	
- Serum Preg ⁺	X																							
- Urine Preg ⁺			X		X	X	X	X	X	X	X			X			X			X			X	
HRCT		X																						X
Spiro/DLCO	X		X [‡]				X		X	X	X	X			X			X			X			X
Biorepository			X															X						X

[†]Screen and Baseline FVC value must be within an absolute difference in percent-predicted of 10% - may repeat within 7 days if not and proceed to enroll if criteria met

^{*}For women of childbearing potential, initial serum pregnancy testing will be carried out with subsequent urine testing at each visit using test kits provided by the study.

*Exit visit will also be carried out within 30 days (±10d) of early termination/withdrawal from the protocol. All subjects who terminate/withdraw early will be encouraged to return for the outcome assessments as detailed above for the 12 month (V15) and 18 month (V21) visits.

**Refer to Protocol Section 17.0 (EMERGENCY DISASTER/ PANDEMIC MANAGEMENT PLAN) for allowed adjustments in the event of a disaster/pandemic that disrupts patient or institutional access.

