5.2.17 Active infection (lung, ulcers or elsewhere) whose management would be compromised by immunosuppression.

5.2.18 Other serious concomitant medical illness (e.g., active malignancy within the past 5 years other than surgically-removed local skin cancer such as a basal cell carcinoma), chronic debilitating illness (other than SSc), unreliability or drug abuse that might compromise the patient's participation in the trial.

5.2.19 Current use, or use within the 30 days prior to their baseline visit, of prednisone (or equivalent) in doses >10 mg/day.

- to avoid increased drug toxicity due to combined immunosuppression.
- subjects who meet all other criteria, but have been on higher doses of prednisone, will be allowed to decrease their prednisone (or equivalent) dose and proceed to the baseline visit at the completion of the 30-day washout.

5.2.20 Smoking of cigars, pipes, or cigarettes during the past 6 months.

- to avoid the increased risk of pulmonary complications and variation in lung function that would be independent from the primary study objectives.

5.2.21 Use of contraindicated medications, including medications with putative disease-modifying properties that do not meet the exposure limits described in Exclusion Criteria #15 and #16, moderate or strong inhibitors of cytochrome P450 (CYP) isozyme 1A2 (CYP1A2) (note

ciprofloxacin allowed up to a dose of 500 mg twice daily), and moderate inducers of CYP1A2 (such as tobacco smoke or phenytoin). See Section 7.5 for complete list.

A study eligibility form will be completed at the end of screening and baseline (i.e., prior to randomization) to assure that all criteria have been met before a subject is eligible for randomization.

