6.1.5 Pre-specified Dose Adjustment & Modifications

The toxicity profiles for MMF and PFD are well established as outlined in Section 2.3 and drug discontinuation and/or dose modification should be managed in a manner consistent with the following criteria in order to provide a nearly uniform response to pre-defined toxicity at all centers. However, in clinical situations that fall outside of these parameters and if warranted based on good clinical practice, a site investigator may independently modify drug dosing as needed to assure patient safety. If such a change is required, the reasons for the deviation are to be documented and the Executive Committee notified within 3 days. Medications that are contraindicated while on treatment with the study drugs are detailed separately in Section 7.5.

In the event that one study drug is permanently discontinued due to tolerability, adverse event or other medical consideration, then continued use of the remaining study drug will be according to the following pre-specified management:

- If only PFD/Plac is permanently discontinued, the participant may continue to take MMF according to the protocol and continue their participation in all study visits according to the normal protocol-defined schedule of events.
- If MMF is prematurely discontinued, the participant must stop the PFD/Plac study medication as well and will be asked to return for key outcome determinations at 12 and 18 months as detailed in Section 5.3.3 (Handling of Premature Participant Withdrawals).

6.1.5.1 Pre-specified dose adjustments for MMF.

The following abnormalities and laboratory test monitoring results require study drug adjustment, either temporary (until normalization) or permanent, as indicated by the nature of the event, its severity and/or course of resolution upon discontinuation of therapy.

- a) Allergic reaction associated with the administration of MMF.

Dose Management: Study drug will be stopped and subject withdrawn from study.

b) Evidence of clinically significant Bone Marrow Suppression including any one or more of the following

- WBC $<2.5 \times 10^3/\mu\text{l}$
- Absolute neutrophil count $<1.0 \times 10^3/\mu\text{l}$
- Platelet count $<100.0 \times 10^3/\mu\text{l}$
- Hemoglobin $< 10.0 \text{ gm/dl}$ or a drop in hemoglobin to $< 9.0 \text{ gm/dl}$ if the baseline hemoglobin was $< 11.0 \text{ gm/dl}$

Dose Management: Management as follows:

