7.5 PROHIBITED MEDICATIONS AND TREATMENTS DURING THE STUDY

7.5.1 Prohibited Medications & Treatments with DMARD Activity

Medications from the following list, and their biosimilars, are prohibited and may not be taken prior to screening in amounts (or for time intervals) that exceed allowable limits as detailed in Exclusion Criteria #15 and #16. They may not be taken while participating in the active drug treatment phase of this study (except for MMF and PFD when specifically administered as study drugs according to the study protocol).

Prior use of these medications must be consistent with Exclusion Criteria #15

a) Oral or short half-life drugs with potential DMARD activity

• Anakinra	• Dasatinib	• Nintedanib
• Apremilast	• Imatinib	• Pirfenidone
• Azathioprine	• Leflunomide	• Pomalidomide
• Baricitinib	• Methotrexate	• Rilonacept
• Cyclophosphamide oral	• Mycophenolate mofetil	• Tacrolimus
• Cyclosporine	• Nilotinib	• Tofacitinib

b) Intravenous or injectable drugs with potential DMARD activity

• Abatacept	• Cyclophosphamide IV	• Rituximab
• Adalimumab	• Etanercept	• Sarilumab
• Alemtuzumab	• Guselukumab	• Secukinumab
• Belimumab	• Golimumab	• Tocilizumab
• Canakinumab	• Infliximab	• Ustekinumab
• Certolizumab	• Ixekizumab	

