7.5.3 Prohibited Medications that may Interfere with Study Drug Absorption/Metabolism

- a) Antacids containing Magnesium and Aluminum Hydroxides **should not** be taken together (at the same time) with MMF due to their impact on the absorption of MMF.
NOTE: Antacids may be used, but should not be taken within 2 hrs of MMF.
- b) Proton Pump Inhibitors (PPIs) **should not** be taken together (at the same time) with MMF due to their impact on the absorption of MMF.
NOTE: PPIs may be used, but should not be taken within 2 hrs of MMF.
- c) Sevelamer and other calcium free phosphate binders **should not** be taken together (at the same time) with MMF due to their impact on the absorption of MMF.
NOTE: Calcium free phosphate may be used, but should not be taken within 2 hrs of MMF.
- b) Cholestyramine **should not** be taken due to interference with enterohepatic recirculation of MMF
- c) Cyclosprine **should not** be taken due to interference with enterohepatic recirculation of MMF
- d) Norfloxacin and Metronidazole **should not** be taken together as a combination therapy while on therapy with MMF due to interference with serum levels of MMF
- e) Ciprofloxacin and/or Amoxicillin plus Clavulanic Acid may temporarily interfere with the enterohepatic recirculation of MMF producing temporary reductions in serum MMF levels.
NOTE: Temporary use for 2 weeks or less is of unclear significance but sustained use of these antibiotics is not recommended.
- f) Ciprofloxacin and other Fluoroquinolones which are moderate inhibitors of CYP1A2 may interfere with the metabolism of PFD, significantly increasing drug exposure.
NOTE: Use of Ciprofloxacin at a maximal dose of 500 mg twice daily for up to two weeks is allowed.
NOTE: If temporary use for Ciprofloxacin at a dose of 750 mg twice daily (or other fluoroquinolone at high dose) is required for 2 weeks or less, the daily dose of PFD should be reduced by 1 capsule three times a day during the period of concomitant use (patients on 3 capsules should reduce to 2, while patients on 2 capsules should reduce to 1)
- g) Rifampin may temporarily interfere with serum levels of MMF.
NOTE: Temporary use for 2 weeks or less is of unclear significance but sustained use of these antibiotics is not recommended.
- h) Fluvoxamine, enoxacin or other strong CYP1A2 inhibitors **should not** be taken due to their impact on the metabolism of PFD, which can significantly increase drug exposure

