- i) Smoking, which is a strong inducer of CYP1A2, is not allowed during the study

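### Exclusion 21 sends readers to Section 7.5 for the full list of contraindicated drugs, but 7.5 omits phenytoin and has no class rule for CYP1A2 inducer drugs or for moderate CYP1A2 inhibitors other than fluoroquinolones

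*Protocol*

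**What the plan says.** Exclusion 21 appears in the Protocol Summary and again as Section 5.2.21. Both versions contraindicate moderate or strong CYP1A2 inhibitors, with ciprofloxacin permitted up to 500 mg twice daily. Both then add moderate inducers and a pointer; the summary reads "moderate inducers of CYP1A2 (such as tobacco smoke, or phenytoin). See Section 7.5 for complete list" and the body text reads "moderate inducers of CYP1A2 (such as tobacco smoke or phenytoin). See Section 7.5 for complete list". SAP 6.2.2 item 21 repeats the criterion, including phenytoin, without the pointer.

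Section 7.5 is titled "PROHIBITED MEDICATIONS AND TREATMENTS DURING THE STUDY". Its CYP1A2 content is three items in 7.5.3:

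- Item f: "Ciprofloxacin and other Fluoroquinolones which are moderate inhibitors of CYP1A2 may interfere with the metabolism of PFD, significantly increasing drug exposure". Short courses are allowed, with a pirfenidone/placebo dose cut at the higher ciprofloxacin dose.
- Item h: "Fluvoxamine, enoxacin or other strong CYP1A2 inhibitors" are not to be taken.
- Item i: "Smoking, which is a strong inducer of CYP1A2, is not allowed during the study".

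Two other sections make 7.5 the on-study reference. Section 6.1.5 says: "Medications that are contraindicated while on treatment with the study drugs are detailed separately in Section 7.5". Section 7.4 has all concomitant medications recorded and checked for compatibility as 7.5 defines it.

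SAP 8.2.2 removes participants from the per-protocol set for a breach of entry criteria or for taking prohibited medications. It does not say which list defines the latter.

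**The concern.** A section cited as the full list should contain at least the drug named in the sentence that cites it, and 7.5 does not contain phenytoin. It also narrows the inhibitor rule: exclusion 21 covers moderate and strong inhibitors, whereas the only class wording for CYP1A2 inhibitors in 7.5 outside the fluoroquinolones is limited to strong ones.

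What is at stake is conduct after randomization. A coordinator who follows Section 7.4 literally and looks up a newly prescribed moderate inhibitor or phenytoin in 7.5 finds no rule and would clear it. For inhibitors the protocol states the hazard itself: 7.5.3 items f and h say that they can raise pirfenidone exposure significantly. For inducers it states no consequence, so none is claimed here.

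There is a possible secondary effect on the per-protocol sensitivity analysis (SAP 10.2.1 item 1), because the meaning of prohibited medications in SAP 8.2.2 is left open.

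**Working it through.** The plan gives no figure on this point, so there is none to reproduce and no formula applies. The check compares each CYP1A2 class in exclusion 21 with every item in Sections 7.5.1 to 7.5.4.

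| Exclusion 21 | Rule in Section 7.5 | Coverage |
|---|---|---|
| Strong CYP1A2 inhibitors | 7.5.3 h: two named drugs plus a class rule | Full |
| Moderate CYP1A2 inhibitors | 7.5.3 f: ciprofloxacin and other fluoroquinolones only | Part |
| Moderate CYP1A2 inducers, with tobacco smoke and phenytoin as examples | 7.5.3 i: smoking only | Part; phenytoin absent |

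One of the three classes is carried in full and two in part.

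The rest of 7.5 does not fill the gap:

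- 7.5.1 lists drugs with potential DMARD activity. Phenytoin is not among them, and none is described as acting on CYP1A2.
- 7.5.2 covers prednisone dose and live vaccines.
- The other items of 7.5.3 concern MMF. Item g, for example, says "Rifampin may temporarily interfere with serum levels of MMF" and does not mention CYP1A2 or pirfenidone.
- 7.5.4 covers hormonal contraceptives and UV exposure.

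Next, where the gap has effect:

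1. **At entry: none.** Exclusion 21 states the three classes and names phenytoin. Section 5.2 requires an eligibility form before randomization. A site need not open 7.5 to apply the criterion.
2. **On study: yes.** Exclusion 21 is an entry criterion. For drugs started later, 7.4 and 6.1.5 both send the reader to 7.5, where the missing classes have no rule.
3. **In the analysis: possible.** SAP 8.2.2 uses the term prohibited medications without citing Protocol 7.5. The title of 7.5 makes it the natural referent, but that link is a reading and is not stated.

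**The case against.** The strongest reply is that the protocol has other protections. Section 2.3.1.3 states an intent to exclude interacting drugs. Section 6.1.5 lets an investigator change dosing on clinical grounds. Section 6.1.5.2 sets dose reductions for adverse events, and Section 7.1.2.4 schedules laboratory monitoring. These stand as backstops. However, the statement of intent names no drug or class, and the dose rules and monitoring mostly act once a problem has appeared.

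It can also be said that phenytoin is the only named drug left out. The documents name no moderate inhibitor beyond the fluoroquinolones and no other inducer drug, so whether further relevant drugs exist cannot be shown from them. That is correct. For the other classes, the gap is in the rule; the documents show no omitted drug. The package inserts in Appendix B might list more, but they are not available here, and exclusion 21 points to 7.5, not to the appendix.

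A reader might infer that the same drug removes a participant from the per-protocol set if present at entry but not if started later. The documents do not establish this. SAP 8.2.2 does not cite 7.5, SAP 9.2 leaves the classification of major deviations to the study team, and per-protocol membership is settled before unblinding. The team could treat on-study phenytoin as prohibited because exclusion 21 calls it contraindicated.

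A reader might also make something of the differing strength labels for smoking in exclusion 21 and 7.5.3 i. They change no decision: exclusion 20 bars smoking in the six months before entry, and 7.5.3 i bars it on study.

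Finally, the fluoroquinolone allowance in 7.5.3 f and 6.1.5.2 g is deliberate and is not part of this gap.

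**Conclusion.** The point holds as an internal inconsistency, at the low end of minor. Section 7.5 is presented as complete and is not: it lacks phenytoin, a class rule for CYP1A2 inducer drugs, and a class rule for moderate inhibitors other than fluoroquinolones. The practical consequence is confined to drugs started after randomization.

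Its size is limited in four ways:

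- The documents give no count of participants who took such a drug, and it may be zero.
- The m-ITT primary analysis and the power do not depend on the list.
- SAP section 14 c reports that enrolment stopped early, so a protocol edit helps only participants still on treatment. The SAP describes much of the study's conduct in the past tense, so there may be few or none.
- The effect on the per-protocol set is possible rather than established.

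The conclusion rests on two assumptions: that sites apply 7.4 as written, and that no list outside the protocol body, such as Appendix B, is used in its place. The exposure concern for unlisted moderate inhibitors extends what 7.5.3 f says of fluoroquinolones as members of that class. The protocol supports no corresponding statement for inducers.

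**What to change.** In Protocol 7.5.3, add two entries:

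- other moderate CYP1A2 inhibitors, keeping the existing short-course fluoroquinolone allowance and the pirfenidone/placebo dose cut;
- moderate CYP1A2 inducers, including phenytoin.

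In SAP 8.2.2, add one sentence saying that prohibited medications means the completed 7.5 list. The study team's classification before unblinding would then treat on-study use of these drugs in the same way as use at entry. If membership has already been fixed, the sponsor can instead state which list was applied.

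The cost is a few lines in the protocol, one sentence in the SAP, and one pass over the concomitant-medication records that Section 7.4 already requires. No new data are needed. SAP 8.1 places finalization before database lock and unblinding, but the documents do not show whether there is still time for the change.
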